#### 4.3 Intervention

All patients will be treated with romidepsin administered intravenously on days 1 and 8 of a 21-day cycle. Lenalidomide will be taken orally daily for days 1-14 of a 21-day cycle. The carfilzomib will be given weekly on days 1, and 8 of a 21-day cycle. Once a MTD is determined this dosing level will be used for the phase Ila portion. Cycles will be continued as above until the patient"s wishes to be removed from the study, unacceptable toxicity develops, disease progression, treating physician recommends removal, or termination of study occurs.

#### 5.1 THERAPEUTIC/DIAGNOSTIC AGENTS

#### 5.2 REVLIMID®

REVLIMID® (lenalidomide), a thalidomide analogue, is an immunomodulatory agent with anti-angiogenic properties. The empirical formula for lenalidomide is  $C_{13}H_{13}N_3O_3$ , and the gram molecular weight is 259.3. The chemical name is 3-(4-amino-1-oxo 1,3-dihydro -2*H*-isoindol-2-yl) piperidine-2, 6-dione and it has the following chemical structure:

Lenalidomide is off-white to pale-yellow solid powder. It is soluble in organic solvent/water mixtures, and buffered aqueous solvents. Lenalidomide is more soluble in organic solvents and low pH solutions. Solubility was significantly lower in less acidic buffers, ranging from about 0.4 to 0.5 mg/ml. Lenalidomide has an asymmetric carbon atom and can exist as the optically active forms S(-) and R(+), and is produced as a racemic mixture with a net optical rotation of zero.

The mechanism of action of lenalidomide remains to be fully characterized. Lenalidomide possesses immunomodulatory and antiangiogenic properties. Lenalidomide inhibited the secretion of pro-inflammatory cytokines and increased

the secretion of anti-inflammatory cytokines from peripheral blood mononuclear cells. Lenalidomide inhibited cell proliferation with varying effectiveness (IC50s) in some but not all cell lines. Of cell lines tested, lenalidomide was effective in inhibiting growth of Namalwa cells (a human B cell lymphoma cell line with a deletion of one chromosome 5) but was much less effective in inhibiting growth of KG-1 cells (human myeloblastic cell line, also with a deletion of one chromosome 5) and other cell lines without chromosome 5 deletions. Lenalidomide inhibited the expression of cyclooxygenase-2 (COX-2) but not COX-1 *in vitro*.

# 5.1.1 Absorption:

Lenalidomide, in healthy volunteers, is rapidly absorbed following oral administration with maximum plasma concentrations occurring between 0.625 and 1.5 hours post-dose. Co-administration with food does not alter the extent of absorption (AUC) but does reduce the maximal plasma concentration (Cmax) by 36%. The pharmacokinetic disposition of lenalidomide is linear. Cmax and AUC increase proportionately with increases in dose. Multiple dosing at the recommended dose-regimen does not result in drug accumulation.

Pharmacokinetic analyses were performed on 15 multiple myeloma patients treated in the phase I studies. Absorption was found to be rapid on both Day 1 and Day 28 with time to maximum blood levels ranging from 0.7 to 2.0 hours at all dose levels (5mg, 10mg, 25mg, and 50mg). No plasma accumulation was observed with multiple daily dosing. Plasma lenalidomide declined in a monophasic manner with elimination half-life ranging from 2.8 to 6.1 hours on both Day 1 and 28 at all 4 doses. Peak and overall plasma concentrations were dose proportional over the dosing range of 5mg to 50mg. Exposure (AUC) in multiple myeloma patients is 57% higher than in healthy male volunteers.

#### 5.1.2 Pharmacokinetic Parameters:

#### Distribution:

In vitro (C)-lenalidomide binding to plasma proteins is approximately 30%.

### Metabolism and Excretion:

The metabolic profile of lenalidomide in humans has not been studied. In healthy volunteers, approximately two-thirds of lenalidomide is eliminated unchanged through urinary excretion. The process exceeds the glomerular filtration rate and therefore is partially or entirely active. Half-life of elimination is approximately 3 hours.

# Supplier(s)

Celgene Corporation will supply Revlimid® (lenalidomide) to study participants at no charge through Celgene"s Revlimid Risk Evaluation and Mitigation Strategy™ (REMS).

# Revlimid REMS Dosage form

Lenalidomide will be supplied as capsules for oral administration.

# **Packaging**

Lenalidomide will be delivered to the center where the prescription will be filled and dispensed. Bottles will contain a sufficient number of capsules for one cycle of dosing.

# Labeling

Lenalidomide supplies are dispensed in individual bottles of capsules. Each bottle will identify the contents as study medication. In addition, the label will bear Celgene's name, quantity contained and the standard caution statement as follows: "Caution: New drug - Limited by Federal law to investigational use." Lenalidomide should not be handled by FCBP unless wearing gloves.

The study drug label must be clearly visible. Additional labels must not cover the Celgene label.

#### Storage

Lenalidomide should be stored at room temperature away from direct sunlight and protected from excessive heat and cold.

# **Special Handling Instructions**

Females of childbearing potential should not handle or administer lenalidomide unless they are wearing gloves.

# Unused study drug supplies

Celgene will instruct the Investigator on the return or destruction of unused study drug. If any study drug is lost or damaged, its disposition should be documented in the source documents. Study drug supplies will be retained at the clinical site pending instructions for disposition by Celgene. Patients will be instructed to return empty bottles or unused capsules to the clinic site.

# 5.1.3 Prescribing Information

Lenalidomide (Revlimid®) will be provided to research subjects for the duration of their participation in this trial at no charge to them or their insurance providers. Lenalidomide will be provided in accordance with the Revlimid REMS® program of Celgene Corporation. Lenalidomide will be delivered to the center

where the prescription will be filled and dispensed. Per standard Revlimid REMS® requirements all physicians who prescribe lenalidomide for research subjects enrolled into this trial, and all research subjects enrolled into this trial, must be registered in and must comply with all requirements of the Revlimid REMS® program. Prescriptions must be filled within 14 days, unless the patient is a female of childbearing potential, in which case the prescription must be filled within 7 days. Only enough lenalidomide for one cycle of therapy will be supplied to the patient each cycle.

# 5.2 Romidepsin

Romidepsin (ISTODAX®) is a unique bicyclic depsipeptide originally isolated from *Chromobacterium violaceum* strain 968. [Ueda H, 1994] Romidepsin is an antineoplastic agent that has been identified as a novel HDAC inhibitor. Romidepsin has been shown to induce hyperacetylation of histones and other nonhistone protein species resulting in a variety of phenotypic changes, induction of the upregulation of gene transcription, G1 and G2/M arrest of the cell cycle, morphological reversion of transformed cells, cell growth inhibition, apoptotic cell death, and inhibition of angiogenesis.

The molecular formula of romidepsin is  $C_{24}H_{36}N_4O_6S_2$ , its molecular weight is 540.71, and its chemical name is: (1S,4S,7Z,10S,16E,21R)-7-ethylidene-4,21-bis(1-methyletheyl)-2-oxa12,13-dithia-5,8,20,23-tetraazabicyclo[8.7.6]tricos-16-ene-3,6,9,19,22-pentone.

In both *in vitro* and *in vivo* systems, romidepsin has been shown to elicit a range of biological activities, including HDAC inhibition, induction or repression of gene expression, cell cycle arrest, differentiation, cell growth inhibition, apoptotic cell death, morphological reversion of transformed cells, and inhibition of angiogenesis. The manner in which romidepsin and other HDAC inhibitors exert their biological effects has not been fully elucidated. The current view is that these agents inhibit, to a greater or lesser extent, the activity of Class I (HDACs 1, 2, 3, 8), Class II (HDACs 4, 5, 6, 7, 9, 10), and Class IV (HDAC 11) HDACs, causing chromatin remodeling and altered gene expression, which results in biological effects that are deleterious to tumor cell growth and survival. There is a growing body of evidence that HDAC

inhibitors can also target substrates other than histones and that the posttranslational modification of cellular proteins by acetylation may play an important role in the biological activities of HDAC inhibitors.

# 5.2.1 Dosage Form

The lyophilized, sterile finished product contains romidepsin, 10 mg/vial and 20 mg/single use vial Povidone, USP, and hydrochloric acid to adjust pH. Romidepsin (for infusion) is supplied in a dual-pack configuration with a single use diluent for romidepsin vial that contains 2 mL of 80% Propylene Glycol, USP, and 20% Dehydrated Alcohol (ethanol), USP; sterile for use in reconstitution of romidepsin (for Infusion).

# 5.2.2 Storage and Handling

The dual pack is to be stored at 20 to 25°C (68 to 77°F), excursions permitted between 15 to 30°C (59 to 86°F) [USP controlled room temperature]. Romidepsin (for infusion) is stable for at least 36 months at 25°C/60% relative humidity (RH) as well as for 6 months at 40°C/75% RH and is stable against heat (for 3 months at 50°C) and humidity (for 3 months at 25°C/83% RH). Appropriately trained personnel using aseptic technique should reconstitute the drug. A volume of 2 mL of reconstitution diluent is added to the lyophilized powder and swirled until contents of the vial are free from visible particles. The reconstituted product stock solution at 5 mg/mL is chemically stable for at least 8 hours at room temperature. However, whenever possible, drug should be prepared within 4 hours of dose administration. A volume of the 5 mg/mL stock solution containing the appropriate dose for the patient will be diluted in 0.9% Sodium Chloride Injection, USP (0.9% saline) for intravenous infusion, as directed by the protocol. This dilution should result in a final drug concentration within the demonstrated stability range of 0.02 to 0.16 mg/mL for reconstituted romidepsin, that is compatible with polyvinyl chloride (PVC), ethylene vinyl acetate (EVA), and polyethylene (PE) intravenous infusion bags; glass bottles may also be used. The romidepsin infusion solution is chemically stable for at least 24 hours at room temperature. However, whenever possible, drug should be prepared within 4 hours of dose administration.

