#### 5.2.3 DRUGS DISPENSATION AND ACCOUNTABILITY

The clinical trial supplies of romidepsin will be provided in a dual pack containing one vial of romidepsin for injection and one vial of diluent. The drug vial will contain a lyophilized powder of 10 mg of lyophilized romidepsin and 20 mg of povidone, USP (used as a bulking agent). The diluent vial will contain 2 mL of a 4:1 mixture of propylene glycol and ethanol. Appropriately trained personnel using an aseptic

technique should reconstitute the drug. A volume of 2 mL of diluent should be added to the lyophilized powder and swirled until contents of the vial are free from visible particles. This provides a stock solution at 5 mg/mL. The stock solution will be diluted using aseptic technique in 500 mL 0.9% Sodium Chloride Injection, USP (0.9% saline) for patients with a body surface area (BSA) ranging from 1.35 to 2.79 m² and in 1000 mL 0.9% saline for patients with a BSA of 2.8 m². Reconstituted drug in saline is compatible with PVC, EVA, and PE IV infusion bags as well as glass bottles. The vials containing the investigational product and the kits they are packaged in will be labeled according to the Good Manufacturing Practice guidelines and the local requirements

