#### **5.3.2 Dose Administration**

- Carfilzomib will be diluted in 100 mL D5W and administered over approximately 30 minutes.
- The dose is calculated using the patient"s actual body surface area (BSA) at baseline. Patients with a BSA greater than 2.2 m^2 should receive a dose based upon a BSA of 2.2 m^2. Dose adjustments do not need to be made for weight changes of less than or equal to 10%. Carfilzomib may be rounded according to local institutional rounding guidelines.
- Prior to each dose of carfilzomib in Cycle 1, give 250 IV normal saline or other appropriate IV fluid before and after carfilzomib administration. At the discretion of the treating physician, give an additional 250 mL to 500 mL of IV fluids as needed following carfilzomib administration. Fluids associated with Romidepsin infusion count toward the 250 mL to 500 mL total volume and may be used as prehydration for carfilzomib. Continue IV hydration, as needed, in subsequent cycles. In patients with chronic kidney disease or history of congestive heart failure, one may consider holding hydration in addition to the romidepsin volume.

- With cycle 1, pre-medicate with dexamethasone 4 mg PO or IV prior to all doses of carfilzomib. Additionally, if dose escalating, please also plan to premedicate with dexamethasone 4mg PO or IV to reduce the incidence and severity of infusion reactions. Reinstate dexamethasone premedication (4 mg PO or IV) if these symptoms develop or reappear during subsequent cycles. Dexamethasone premedication dosing has been increased to 8 mg PO or IV in clinical trials where the carfilzomib dose has exceeded 45 mg/m².
- It is preferred that carfilzomib is given after romidepsin.
- The Initial dose of carfilzomib given to any given patient (cycle 1, day 1) will be 20mg/m^2 regardless of the dose level. Subsequent doses will be based on the patient dose level.

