#### Treatment Plan: carfilzomib/romidepsin/lenalidomide Phase Ila

The phase IIa portion is planned to include 20 patients. Each disease cohort, B-and T-cell lymphoma, will have 10 patients. Patients treated at MTD in the phase Ib cohort (if measurable disease at enrollment) will be included towards the 20 patient total in the phase IIa. The MTD has been determined to be dose level 1; 8 mg/m² romidepsin on days 1 and 8, 15 mg lenalidomide from days 1 - 14, and 36 mg/m² carfilzomib on days 1 and 8. The phase IIa cohort will be evaluated both collectively and by disease subtype.

Patients that have received long-term therapy (greater than one year) with response will be allowed to have their schedule modified to allow less frequent dosing per investigator and primary investigator discretion.

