# 9.5.2 Instructions for Dose Modifications or Interruption During Phase 1 Cycle 2 and beyond and phase 2 all cycles

Dose delay and dose reduction rulesare as follows and in the table below. The following dose modification criteria are applicable to adverse events related to study drugs:

- In the event of dose reduction due to toxicity all agents will be reduced as per Table 2, 3, 4. If an agent is already at its lowest dose per tables 2,3,4 then the other agents will be reduced. If the lowest doses are not tolerated the subject will be removed from the study.
- For treatment interruptions during a cycle, the 21-day schedule of each cycle will continue to be followed. Missed doses of lenalidomide, carfilzomib and romidepsin are not made up. For treatment interruptions that delay the scheduled start of a new cycle, when toxicity has resolved as required to allow the start of a new cycle, the restart day of therapy becomes Day 1 of the next cycle.
- If a patient is at the lowest dose level and deriving benefit from therapy, they may continue on protocol therapy despite ≥ grade 3 hematologic toxicity or non-clinically significant non-hematologic toxicity after discussion with the MSK principal investigator. A delay of planned study therapy of greater than 21 days with result in removal from study.

TABLE 2: Lenalidomide Dose Modification Steps		
Current Lenalidomide Dose	One Level Dose Reduction	
20 mg daily on Days 1-14 every 21 days	15 mg daily on Days 1-14 every 21 days	
15 mg daily on Days 1-14 every 21 days	10 mg daily on Days 1-14 every 21 days	
10 mg daily on Days 1-14 every 21 days	5 mg daily on Days 1-14 every 21 days	

TABLE 3: Romidepsin Dose Modification Steps		
Current Romidepsin Dose	One Level Dose Reduction	
10 mg/m  daily on Days 1,8	8 mg/m² daily on Days 1,8	
8 mg/m² daily on Days 1,8	5 mg/m² daily on Days 1,8	
5 mg/m² daily on Days 1,8	5 mg/m² daily on Days 1	
Carfilzomib Dose Modification Steps		
Current Carfilzomib Dose	One Level Dose Reduction	
56 mg/m 	45 mg/m 	
45 mg/m 	36 mg/m 	
36mg/m 	20 mg/m 	

TABLE 4: Dose Modifications for Lenalidomide, Carfilzomib and Romidepsin for Phase 1 cycle 2 and beyond/ Phase 2 all cycles		
NCI CTC Toxicity Grade	Dose Modification Instructions	
, , ,	(also see Instructions for Initiation of a New Cycle above)	

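### At the reduced romidepsin dose of 5 mg/m², the fixed saline volumes in Section 5.2.3 give an infusion below the stability range in Section 5.2.2 for BSA 1.35 to under 2.0 m² and at 2.8 m²

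*Combined protocol and SAP*

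**What the plan says.** Section 5.2.2 (Storage and Handling) has the required amount of stock diluted in "0.9% Sodium Chloride Injection, USP (0.9% saline) for intravenous infusion, as directed by the protocol", and says the result should be a "final drug concentration within the demonstrated stability range of 0.02 to 0.16 mg/mL for reconstituted romidepsin".

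Section 5.2.3 (Drugs Dispensation and Accountability) supplies that direction. The 10 mg vial is reconstituted with 2 mL of diluent ("This provides a stock solution at 5 mg/mL"). The stock is then added to 500 mL of saline "for patients with a body surface area (BSA) ranging from 1.35 to 2.79 m²", or diluted "in 1000 mL 0.9% saline for patients with a BSA of 2.8 m²". Dose does not enter the rule.

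The Phase IIa treatment plan states: "The MTD has been determined to be dose level 1; 8 mg/m² romidepsin on days 1 and 8". In Table 3 (Section 9.5.2, dose modifications for phase 1 cycle 2 onward and all phase 2 cycles), the step below 8 mg/m² is "5 mg/m² daily on Days 1,8". The step after that keeps 5 mg/m² but on day 1 only. The same section says that a reduction for toxicity lowers all three agents together.

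**The concern.** The volume rule fits the escalation doses but takes no account of the lower dose that Table 3 introduces. A smaller dose in an unchanged bag is a more dilute infusion, and the margin at 8 mg/m² is already thin at the low end of the BSA band.

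A pharmacy that follows Section 5.2.3 at 5 mg/m² may prepare a bag outside the only concentration range the protocol describes as demonstrated. A pharmacy that follows Section 5.2.2 must depart from the stated volume. In a multicenter trial, sites could settle this differently.

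The dose is reached easily: 5 mg/m² is the first reduction from the MTD. Because all agents are lowered together, toxicity from lenalidomide or carfilzomib can also bring a patient to it. Treatment continues until progression or unacceptable toxicity, so one patient may receive many such bags.

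**Working it through.** **Inputs**

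- Required concentration: 0.02 to 0.16 mg/mL (Section 5.2.2).
- Volume: 500 mL for BSA 1.35 to 2.79 m²; 1000 mL for BSA 2.8 m² (Section 5.2.3).
- Stock: 5 mg/mL (Section 5.2.3).
- Doses: 8 and 10 mg/m² (Table 1); 5 mg/m² after reduction (Table 3).

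**Check of the plan's own figure.** Stock = 10 mg / 2 mL = 5 mg/mL, as stated.

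**Formula.** Concentration (mg/mL) = dose (mg/m²) × BSA (m²) / volume (mL).

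**Escalation doses**

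| Dose (mg/m²) | BSA 1.35, 500 mL | BSA 2.79, 500 mL | BSA 2.8, 1000 mL |
|---|---|---|---|
| 8 | 10.8/500 = 0.0216 | 22.32/500 = 0.0446 | 22.4/1000 = 0.0224 |
| 10 | 13.5/500 = 0.0270 | 27.9/500 = 0.0558 | 28/1000 = 0.0280 |

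All are in range. The lowest dose these volumes can support is 0.02 × 500 / 1.35 = 7.41 mg/m² at BSA 1.35, and 0.02 × 1000 / 2.8 = 7.14 mg/m² at BSA 2.8.

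**Reduced dose, 5 mg/m²**

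| BSA (m²) | Volume (mL) | Concentration (mg/mL) | Shortfall below 0.02 |
|---|---|---|---|
| 1.35 | 500 | 6.75/500 = 0.0135 | 32.5% |
| 1.7 | 500 | 8.5/500 = 0.0170 | 15% |
| 1.8 | 500 | 9.0/500 = 0.0180 | 10% |
| 1.9 | 500 | 9.5/500 = 0.0190 | 5% |
| 2.0 | 500 | 10/500 = 0.0200 | none (at the limit) |
| 2.79 | 500 | 13.95/500 = 0.0279 | none |
| 2.8 | 1000 | 14/1000 = 0.0140 | 30% |

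The crossover in 500 mL is BSA = 0.02 × 500 / 5 = 2.0 m².

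**Sensitivity to the stock volume.** At 5 mg/m² the added stock is 5 × BSA / 5 = BSA mL. Counting it gives 6.75/501.35 = 0.01346 at BSA 1.35 and 14/1002.8 = 0.01396 at 2.8. The crossover becomes 10/4.98 = 2.008 m². Nothing material changes.

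**Volume that would comply.** At 5 mg/m², volume ≤ 5 × BSA / 0.02 = 250 × BSA mL: 337.5 mL at BSA 1.35, 425 mL at 1.7 and 700 mL at 2.8. With the stock counted in the total, the saline ceiling is 249 × BSA mL.

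**The case against.** The arithmetic is not in dispute. The case on the other side concerns weight and wording.

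- **No harm is shown.** The documents do not say the drug degrades below 0.02 mg/mL, and they advise preparing it within 4 hours of use where possible. This stands. It limits the finding to preparation outside the demonstrated range. Section 5.2.2 also says the infusion solution is stable for at least 24 hours, but that most naturally refers to solutions within the range, so it does not cover 0.0135 mg/mL.
- **The concentration requirement is worded softly.** Section 5.2.2 says what the dilution should achieve, so a pharmacist has a target to check the bag against and might adjust. But that section also defers to the protocol for the dilution, and Section 5.2.3 then fixes the volume without exception. I found no passage that gives a smaller volume or says which instruction prevails.
- **The 2.8 m² entry may have lost a ≥ sign in text extraction.** This is plausible. On that reading the shortfall at 2.8 m² remains, and it extends to every BSA below 4.0 m² (0.02 × 1000 / 5).
- **Only reduced patients are affected.** This is correct, and their number cannot be estimated from the documents.

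**Conclusion.** The inconsistency is real. At 5 mg/m² the stated volumes give 0.0135 to just under 0.02 mg/mL for BSA 1.35 to under 2.0 m², and 0.014 mg/mL at 2.8 m². From 2.0 to 2.79 m² the bag is in range, apart from a 0.01 m² shift in the crossover if the stock volume is counted. Both escalation doses are in range at every listed BSA. Below 1.35 m² Section 5.2.3 states no volume, so nothing is claimed there.

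The number of patients involved is unknown, because the documents give neither a BSA distribution nor an expected reduction rate; phase IIa plans 20 patients. No loss of delivered dose is shown, and no sample size, stopping rule, endpoint or analysis is affected. It is a minor point in practice, but it is an error in a preparation instruction, it arises at the first dose reduction, and it should be corrected.

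**What to change.** Amend Section 5.2.3 so that the volume depends on dose as well as BSA, with a ceiling of 250 × BSA mL at 5 mg/m². One workable choice is 250 mL for BSA 1.35 to 2.79 m² (6.75/250 = 0.027 to 13.95/250 = 0.056 mg/mL) and 500 mL at 2.8 m² (14/500 = 0.028 mg/mL). Alternatively, state in Section 5.2.3 that the volume must be chosen to give 0.02 to 0.16 mg/mL. The documents support the ceiling; the particular bag sizes are a suggestion that pharmacy and the manufacturer should confirm. The amendment should also say whether 1000 mL is meant for BSA of 2.8 m² and above.

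The cost is a short pharmacy amendment and a check against Section 5.3.2, which provides: "Fluids associated with Romidepsin infusion count toward the 250 mL to 500 mL total volume and may be used as prehydration for carfilzomib". A 250 mL bag supplies 250 mL less than the current 500 mL bag, so separate carfilzomib hydration fluid may be needed. That effect is narrow. Fluid before and after carfilzomib is mandatory only in cycle 1, and later cycles are as needed. Phase Ib allows no reductions in cycle 1, so mandatory hydration could coincide with the reduced dose only on day 8 of cycle 1 in phase IIa.
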